12.4 Collection and Recording of Adverse Events

Adverse events (including SAEs) will be collected from the time of consent until a subject completes study participation or until 30 days after he/she prematurely withdraws (without withdrawing consent) or is withdrawn from the study.

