We will be recruiting a total of 136 participants, between the ages of 18-60. Participants will be enrolled in this study based on the presence of active eosinophilic esophagitis and adherence to the inclusion and exclusion criteria. We intend to conduct a prospective non-blinded randomized trial that compares a 1-food elimination diet (1FED) versus a 6-food elimination diet (6FED) for six weeks (Phase 1). Subsequently, non-responders to 1FED dietary elimination therapy will be treated with 6FED and non-responders to 6FED will be treated with SGC (swallowed fluticasone at a dose of 880 mcg twice a day) for six weeks (Phase 2) while on an unrestricted diet, if the participant chooses to continue in to Phase 2. The empiric dietary therapy interventions are as follows: 1-food elimination diet (1FED)—avoidance of milk vs. 6-food elimination diet (6FED)—avoidance of milk, egg, wheat, soy, fish/shellfish, and peanut/tree nuts, for six weeks. Milk elimination for both 1FED and 6FED includes all mammal milk (i.e. goat, sheep, and cow's milk must all be eliminated). The study design is shown schematically in Figure 1 Study Design Flowchart.

In Phase 1, participants will be randomized 1:1 to either 1 food elimination (milk elimination alone, 1FED) or 6 food elimination (milk, egg, wheat, soy, fish/shellfish, peanut/tree nuts elimination, 6FED) therapeutic diet. At the end of this phase, an EGD will be performed to assess remission. Attainment of remission (esophageal eosinophil counts <15 eosinophils/high powered field) after Phase 1 will result in study discontinuation and maintenance of the “successful” dietary therapy. Treatment non-responders may choose whether or not to continue into Phase 2. Dietary therapy non-responders who were on 6FED in Phase 1 and continue on to Phase 2 will receive topical swallowed steroids for six weeks (Phase 2) followed by EGD with esophageal biopsies. These participants will return to an unrestricted diet (i.e. stop 6FED) prior to beginning topical swallowed steroid therapy. Dietary non-responders in Phase 1 who were on 1FED and continue on to Phase 2 will continue to a 6FED

[figure not shown]
Version 10/14/2019

therapeutic diet (Phase 2) for six weeks followed by EGD with esophageal biopsies to assess remission.

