Adverse events (AE) that occur during Phase 1 and Phase 2 will be summarized within each treatment group using frequency and percent of patients with at least 1 occurrence and total number of occurrences (nAEs). These summaries will be done by SOC/AE level using the CTCAE 4.0 system. The percentage of patients experiencing at least one occurrence of an AE at the SOC/AE level will be compared using Fisher's Exact Test.

Software Used (with References) and Specialized Macros (with References)

SAS version 9.4

This SAP has been reviewed and approved by:

Investigator

Date

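### The SAP's Fisher's tests on adverse events are not limited to Phase 1, and any version that uses Phase 2 data is not a fair comparison of the two diets

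*SAP*

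**What the plan says.** The SAP's Adverse Events section has a descriptive sentence and a testing sentence.

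- Descriptive: "Adverse events (AE) that occur during Phase 1 and Phase 2 will be summarized within each treatment group", as patients with at least one occurrence and as total occurrences.
- Testing: "The percentage of patients experiencing at least one occurrence of an AE at the SOC/AE level will be compared using Fisher's Exact Test".

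The testing sentence names no phase. The section does not say whether treatment group means randomised arm or treatment received, and it makes no adjustment for time at risk. Section 13 of the protocol contains no AE comparison that would settle the reading. By contrast, the SAP ties its primary and secondary treatment comparisons to the end of Phase 1.

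The SAP's Study design section says who is observed in Phase 2 and on what treatment:

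- Remission "after Phase 1 will result in study discontinuation and maintenance of the" successful diet, so responders leave.
- "Treatment non-responders may choose whether or not to continue into Phase 2".
- In Phase 2, "non-responders to 1FED dietary elimination therapy will be treated with 6FED and non-responders to 6FED will be treated with SGC".
- For those who go on to SGC: "These participants will return to an unrestricted diet (i.e. stop 6FED) prior to beginning topical swallowed steroid therapy".

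Under Protocol 12.4, adverse events "will be collected from the time of consent until a subject completes study participation".

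**The concern.** Randomisation protects the diet comparison only in Phase 1. After that, whether a patient is still observed depends on failing the assigned diet and choosing to continue, and nobody who continues stays on the Phase 1 treatment. An AE comparison that includes Phase 2 can be built in three ways, and none of them compares the diets.

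- **Randomised arm, phases pooled.** The arm with more failures is observed longer, and SGC events are counted in the 6FED arm. This compares 1FED-then-6FED with 6FED-then-SGC.
- **Treatment received.** A 1FED non-responder who continues counts under both 1FED and 6FED. The groups overlap, and Fisher's test requires independent groups.
- **Phase 2 alone.** This compares 6FED with SGC among self-selected non-responders to different diets, with no 1FED group. Protocol 13.4.6 itself allows for substantial imbalance between the Phase 2 groups.

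At stake is whether the AE table can be read as evidence about the diets. Differences in follow-up, or steroid effects such as oral thrush (Protocol 6.1), could be read as diet effects, and a real diet difference could be diluted.

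**Working it through.** **Inputs from the documents.** Remission of 45% (1FED) and 70% (6FED), and 68 randomised per arm (Protocol 13.6). Each phase lasts 6 weeks. The Phase 2 visit is at Week 10, within 4 weeks of the EGD, and Phase 2 ends at Week 16 (Protocol 9.5, 9.7).

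**Assumptions, because the documents give no figure.** Phase 2 uptake u of 50-100%; 6-week AE risk r of 2-40%; nominal two-sided 0.05 for the AE test; AE risk unrelated to response; no dropout. Time at risk T for continuers is 12 weeks (on treatment only) or 16 weeks (full calendar window).

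**The plan's own figure.** No AE rate or AE power is stated. The remission rates do support the stated sample size: exact enumeration of the likelihood ratio test at 60 per group gives 80.6% power, against the stated minimum of 80%.

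**Step 1: who can enter Phase 2.** 68 × 0.55 = 37.4 from 1FED and 68 × 0.30 = 20.4 from 6FED. At 50% uptake these become 18.7 and 10.2.

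**Step 2: mean follow-up**, 6 + (T − 6) × f × u, with f = 0.55 or 0.30.
- T = 12, u = 0.5: 7.65 v 6.90 weeks.
- T = 16, u = 1: 11.5 v 9.0 weeks.

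**Step 3: pooled by randomised arm, same weekly hazard on every treatment.** With h = −ln(1 − r)/6, P(at least one AE) = 1 − [(1 − fu)·exp(−6h) + fu·exp(−Th)]. The false gap is therefore 0.25 × u × [exp(−6h) − exp(−Th)]. Rejection rates are exact enumerations of Fisher's test at 68 v 68.

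| 6-week risk | T (weeks) | Uptake | 1FED v 6FED | Gap (points) | Rejection, pooled | Rejection, Phase 1 only |
|---|---|---|---|---|---|---|
| 2% | 12 | 50% | 2.5% v 2.3% | 0.2 | 0.3% | 0.1% |
| 5% | 16 | 100% | 9.3% v 7.3% | 1.9 | 3.3% | 1.3% |
| 20% | 12 | 100% | 28.8% v 24.8% | 4.0 | 5.7% | 3.1% |
| 20% | 16 | 70% | 29.6% v 25.2% | 4.3 | 6.2% | 3.1% |
| 20% | 16 | 100% | 33.7% v 27.5% | 6.2 | 9.2% | 3.1% |
| 40% | 16 | 50% | 49.5% v 45.2% | 4.3 | 5.4% | 3.2% |
| 40% | 16 | 100% | 58.9% v 50.3% | 8.6 | 12.7% | 3.2% |

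**Step 4: an event caused only by SGC, at risk s.** It adds 0.30 × u × s to the 6FED arm: 0.30 × 0.5 × 0.10 = 1.5 points up to 0.30 × 1 × 0.30 = 9.0 points. This runs opposite to Step 3.

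**Step 5: dilution of a real diet difference.** Assume per-phase risks of 10% on 1FED, 30% on 6FED and 0-30% on SGC.
- SGC 0%, u = 1: 1FED arm 1 − 0.90 × (1 − 0.55 × 0.30) = 24.85%; 6FED arm 30%; gap 5.15 points.
- SGC 30%, u = 0.5: 1FED arm 1 − 0.90 × (1 − 0.275 × 0.30) = 17.4%; 6FED arm 1 − 0.70 × (1 − 0.15 × 0.30) = 33.2%; gap 15.7 points.

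The Phase 1 gap is 20 points with 80% power. Pooled power is 7% to 49%.

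**Step 6: by treatment received.** The 6FED group would hold 68 + 18.7 = 86.7 to 68 + 37.4 = 105.4 patients. Of these, 18.7/86.7 = 22% to 37.4/105.4 = 35% were not randomised to 6FED. Between 27.5% and 55% of 1FED patients would count in both groups.

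**The case against.** The strongest reply is that the SAP never says the phases will be pooled. Both phases are named only in the descriptive sentence. A phase-by-phase analysis is a natural reading, because treatments differ by phase and the SAP already summarises Phase 2 remission separately by Phase 1 treatment. Its Phase 1 part would be exactly the fair comparison. This stands: a reader might infer a stated plan to pool, and the text does not support that. But the wording does not exclude pooling or a Phase 2 test either, and it lacks the end-of-Phase-1 limit used for efficacy.

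A reader might also take the 9-13% rejection rates as the expected error. They need full uptake, 16 weeks at risk and 6-week risks of 20-40%. The tests run at organ-class and event level, where many rows will be rarer; at 5% or below, rejection stays under the nominal 5% in every scenario run.

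It is equally tempting to conclude that the less effective diet will look less safe. Longer follow-up raises 1FED, SGC events raise 6FED, and the documents do not show which prevails.

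Two further points stand. Pooling by randomised arm is a valid comparison of the two treatment sequences, though not of the diets. And no stated objective compares the diets' safety, so this is a supporting table and not a main conclusion of the trial.

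**Conclusion.** The concern holds as a missing restriction on the AE test. The SAP leaves open comparisons that use Phase 2 data, and each of them is confounded or invalid as a comparison of the diets. Only Phase 1 by randomised diet is fair.

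The size cannot be fixed from the documents. Under the stated assumptions, pooling by arm with equal hazards gives a false gap of about 0.2 to 8.6 points (1FED higher) and rejection from under 1% to about 13%, against about 0-3% for Phase 1 only. An SGC-only event moves the comparison the other way by 1.5 to 9.0 points, so the net direction is uncertain. False positives are a modest risk over most of the range. Dilution of a true diet difference can be larger. If the sponsor already intends to test by phase, the Phase 1 result is sound and only the Phase 2 test needs to go.

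**What to change.** Amend the SAP's Adverse Events section as follows:

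1. Limit the between-group Fisher's tests to events with onset from randomisation to the Phase 1 end-of-treatment EGD, grouped by randomised diet.
2. Tabulate later and Phase 2 events descriptively, separately for 1FED-to-6FED and 6FED-to-SGC, with weeks at risk and no between-group test.

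The window should close at the EGD. Protocol 11.1 defines completion by that EGD, while Protocol 4.2 ties a responder's completion to the central pathology read. Equal AE collection after the EGD in responders and non-responders is therefore not assured.

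The cost is a few sentences and the use of AE onset dates, with no change to sample size. There would be no Phase 2 p-value, and events after the Phase 1 EGD would be described but not tested.
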